6.1. Device description

The Cefaly® device is a small, portable product, which is meant to be worn on the forehead by attachment to a self-adhesive electrode. A rechargeable battery provides power to the Cefaly®

device. The Cefaly® generates very precise electrical impulses that permit stimulation of the nerve

fibers. The device acts by stimulation of the upper branch of the trigeminal nerve.

The device has been approved by the FDA as a class II therapeutic device, indicated for the

prophylactic treatment of episodic migraine in patients 18 years of age or older.

The Cefaly® device (Figure 2) is comprised of the following specifications:

• Dimensions: 55 mm x 40 mm x 15 mm

• Weight: 12 g.

Figure 2 - Cefaly® device

The Cefaly® device is connected to the body via a self-adhesive electrode (Figure 3) applied on the forehead. The device specific for the trial will run one "training session" of 20 minutes and one treatment session of 120 minutes. The Cefaly® electrode is 94 mm long and 30 mm high. It makes the interface between the Cefaly® device and the skin. This electrode has been approved by the FDA together with the Cefaly® device.

Figure 3 - Cefaly® electrode

# 6.2. Device technology

The Cefaly® is an external cranial neurostimulator designed for supraorbital neurostimulation (also known as external trigeminal nerve stimulation: e-TNS). Trigeminal nerve stimulation induces a sedative effect on the central nervous system (1).

The Cefaly® generates electrical impulses that are transmitted transcutaneously via a bipolar self-adhesive electrode placed on the forehead.

The Cefaly® operates on direct electrical energy, which is output from one rechargeable battery.

The Cefaly® Abortive Program delivers electrical energy in the form of rectangular biphasic pulses. The intensity is increasing linearly to reach a maximum of 16 mA after 14 minutes (and then stays constant for 106 minutes). The pulse frequency is 100 Hz. The pulse width is 250 µs.

The supraorbital electrode is designed in order to cover both sides of the supratrochlearis and supraorbitalis nerves, which are branches of the trigeminal nerve (Figure 4).

The electrical impulses generated by the Cefaly® device are transmitted transcutaneously via the supraorbital electrode to excite (trigger action potentials) the supratrochlearis and supraorbitalis nerves. Supratrochlearis and supraorbitalis (or supratrochlear and supraorbital) nerves belong to the upper branch of the trigeminal nerve (V1). Therefore, the supraorbital neurostimulation is also known as external trigeminal nerve stimulation.

[figure not shown]

Figure 4 - The Cefaly® electrode placed on the forehead covers the supratrochlearis and supraorbitalis nerves

#### 6.3. Mechanism of action

The Cefaly® device generates electrical impulses. Electrical impulses get out of the device via 2 metallic contacts. Contacts are in connection with 2 conductive areas on the self-adhesive electrode. The self-adhesive electrode is applied on the forehead. Therefore, electrical impulses generated by the Cefaly® device are running through the metallic contacts then through the electrode in order to carry out excitation on the nerve fibers just located under the forehead skin i.e. supratrochlearis and supraorbitalis (or supratrochlear and supraorbital) nerves which belong to the trigeminal nerve. Consequently, electrical impulses generated by the Cefaly® trigger signals (action potentials) on supratrochlear and supraorbital nerves or trigeminal nerve. Repetitive excitation of trigeminal nerve is a neuromodulation of the trigeminal system. Neuromodulation of the trigeminal system induces a sedative effect on the central nervous system and a trigeminal nociceptive threshold modification.

#### 6.4. Use during the trial

Indications for use: abortive treatment of migraine with or without aura in patients 18 years of age or older.

The patient will apply the Cefaly® Abortive Program device for a first 20-minute training session to check his/her ability to use the device appropriately. Then, at home, the patient will apply the Cefaly® Abortive Program device for a 120-minute session during a qualifying migraine attack. Duration, intensity and/or interruption will be recorded for each patient thanks to a built-in electronic system in the device.

#### 6.5. Medication during the trial

Patients will be instructed to not take any acute anti-migraine medication during the acute treatment phase. After the 2 hours acute treatment phase, if the patient has moderate or severe migraine

headache pain (Grade 2 or 3), he/she is allowed to take his/her own anti-migraine rescue medication. Use of acute medication will be recorded by the patient on the diary for the 24 hours following the beginning of the treatment.

# 6.6. Device provisioning

The promoter will deliver the specific Cefaly® Abortive Program devices and related accessories directly to the investigators. A single device will be delivered to each patient that cannot be reused on different patients. Each Cefaly® Abortive Program device will bear a unique number that has to be reported in the patient's CRF and will allow to identify, at the end of the study, which device was used by each patient.

Investigational clinical devices are to be dispensed only in accordance with the protocol. The investigator is responsible for keeping accurate records of the clinical supplies received from the promoter, the amount dispensed and returned, and the amount remaining at the conclusion of the study.

# 7. Practical study modalities

# 7.1. Efficacy outcome measures

The treatment efficacy outcomes will be assessed based on the following clinical data.

- **Headache pain severity.** In order to evaluate the modification of pain severity from baseline to 2-hour and 24-hour time points, patients will be asked to note their headache pain intensity on the following scale: 0 = no pain; 1 = mild pain; 2 = moderate pain; 3 = severe pain.
- **Migraine associated symptoms**. The patient will also note the presence of migraine associated symptoms (photophobia, phonophobia, nausea, vomiting) and will specify which associated symptom is the most bothersome symptom (MBS).
- **Rescue medication intake**. The patient will also record whether he/she took ANY acute rescue medication during the 24 hours following the beginning of the e-TNS session.

The following table depicts when the different measures will be made:

	At baseline, i.e. just before the beginning of the e-TNS session	2 hours after the beginning of the e-TNS session	24 hours after the beginning of the e-TNS session
Headache pain severity	•	•	•
Migraine associated symptoms	•	•	•
Most bothersome migraine associated symptom (MBS)	•		
Rescue medication intake			•

All clinical data will be collected on a paper diary and AE collecting form.

## 7.2. Calendar

The study is foreseen to start in June 2017 and to be finished by December 2017.

8. Data management and statistics

8.1. Data management

Each patient who signs a consent form to participate in the study will be assigned a unique number for identification purposes. Each patient should be assigned only one number. Should the patient fail to

qualify for the study, his/her baseline number must not be re-used for any other patient in the study.

CRF and documents provided to the patient (diary and AE collecting form) will include the unique

patient number in the header.

The collected data will be included in the case report form (CRF) and in patient diary. These completed

documents will be provided by the investigator to the promoter. In practice, the investigator records

these completed documents in an appropriate binder and sends the scan of the documents by email

to the promoter. Tracking of completed source documents is performed: when a patient completed

the clinical investigation but the related source documents have not been received, an email is sent to

the investigator/study coordinator to request missing documents.

Duration, intensity and/or interruption of the treatment are recorded for each patient thanks to a built-in

electronic system in the device. Each device will bear a unique number that has to be reported in the

patient's CRF and will allow to identify which device was used by each patient.

In case of lack of data accuracy (missing data, unclear data, discrepancies), a data clarification query

is sent to the investigator. The completed and signed form is sent back to the promoter. Tracking of

data clarification forms is performed to ensure that all data clarification forms are completed by the

investigator/study coordinator.

AE and SAE are collected on the paper CRF. Investigators will report SAE and AE on the specific forms

annexed to the CRF. These SAE and AE forms will be reviewed and analysed by the promoter when

received.

8.2. Statistics

The statistical analysis of the data obtained from this study will be the responsibility of the promoter.

8.2.1. Sample size

The sample size was computed based on the primary outcome, i.e. pain freedom at 2 hours. Results

from previous sham-controlled trial using the Cefaly® device as acute treatment of migraine reported

7,7% of pain freedom at 2 hours in the placebo group. In the current study, the pain freedom at 2 hours

associated with the Cefaly® Abortive Program treatment is expected to be similar to the results related to triptans, in particular to Lasmiditan that presented 32,2% of pain freedom at 2 hours.

A power analysis showed that a sample of 42 patients allows detecting a statistically significant difference between the expected (32,2%) and placebo (7,7%) pain freedom at 2 hours with a power of at least 80% and a 5% level of significance.

Taken into account a rate of 30% of patient loss during the study (based on the Lasmiditan study), at least 60 patients should be included in the study.

#### 8.2.2. Statistical methods

- All relevant general, safety and efficacy data will be descriptively summarized at each time point.
- Continuous data will be summarized by the number of subjects (N), the arithmetic mean, the standard deviation, the coefficient of variation as a percentage (CV%), the median, the interquartile range, the minimum and the maximum value.
- Categorical data will be summarized by absolute (N) and relative (%) frequency tables.
- Where considered as relevant, the study data will also be graphically depicted.
- For each patient, the outcomes will be calculated according to all data available, and if necessary, imputation of missing data will be performed according to the last value carried forward method.
- Unless otherwise stated, all statistical tests will be conducted at the  $\alpha$ =0.05 (2-sided) level.

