#### **Secondary outcomes:**

- 1. Pain Relief (PR) at 2 hours, defined as the percentage of patients having a reduction of a moderate or severe migraine headache (Grade 2 or 3) at baseline to a mild headache or to no headache (Grade 1 or 0) at 2 hours after the beginning of the e-TNS session.
- 2. Percentage of patients with absence of photophobia, phonophobia, nausea, vomiting at 2 hours after the beginning of the e-TNS session.
- 3. Use of rescue medication between 2 and 24 hours, defined as the percentage of patients who took acute anti-migraine medication between 2 and 24 hours after the beginning of the e-TNS session.
- 4. Sustained pain freedom at 24 hours, defined as the percentage of patients having no headache (Grade 0) at 2 hours, with no use of rescue medication and no relapse of headache pain within the 24 hours after the beginning of the e-TNS session.

Note: The baseline corresponds to the beginning of the e-TNS session.

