4.2.5. Discontinuation

**Withdrawal** 

Patients may withdraw their consent at anytime during the study. If a patient wishes to discontinue from the study but no discontinuation visit is performed (e.g., patient refuses to return to the study site), then the patient should be formally discontinued from the study on the day the decision to discontinue is

made.

Lost to follow-up

All attempts must be made to contact a patient who is lost to follow-up. Patients who are lost to follow-up should be formally discontinued from the study on the day of the last unsuccessful attempt at

contact.

Absence of qualifying migraine

If a patient has not treated a qualifying migraine attack within two months of the screening visit, he/she will be discontinued from the study and study material will have to be returned to the study site.

Notification and practical modalities

At a minimum, for any patient who discontinues the study, the patient status must be completed in the CRF. When a patient discontinues prior to study completion, all applicable activities scheduled for the final study visit should be performed at the time of discontinuation. In particular, patients are required to return the Cefaly® Abortive Program device.

[figure not shown]

Figure 1 - Study flowchart

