#### 8.2.3. Statistical analysis

Modified intention-to-treat (mITT) analysis

Patient data will be included in the mITT analysis if all the four following conditions are met:

- 1. The patient treated a qualifying migraine.
- 2. The patient applied the Cefaly® Abortive Program treatment during at least one minute\*.
- 3. The headache pain severity score **AND** the migraine associated symptom(s) at baseline were reported in the diary.
- 4. The headache pain severity score **OR** the migraine associated symptom(s) at 2 hours were reported in the diary.

Data provided by Colucid Pharmaceuticals, Inc. and available on the following website: https://globenewswire.com/news-release/2016/09/06/869611/0/en/CoLucid-Pharmaceuticals-Announces-Achievement-of-Both-Primary-and-Key-Secondary-Endpoints-in-the-SAMURAI-Phase-3-Pivotal-Trial-of-Lasmiditan-in-Migraine.html (consulted in May 2017).

\*If the patient stopped the 2-hour treatment session before its end for any reason, he/she is kept in the modified intention-to-treat (mITT) analysis if all the other conditions are met.

If the patient takes rescue medication between 2 hours and 24 hours after the beginning of the e-TNS session, the headache pain intensity and associated symptoms presence can be affected by the medication and the last value carried forward method (2-hour value carried forward method in this case) will be applied for the 24-hour time point headache pain severity and migraine associated symptoms.

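### For a patient pain-free at 2 hours with no 24-hour pain grade, last value carried forward supplies the 'no relapse' part of sustained pain freedom by imputation, and no rule covers a blank rescue record

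*Combined protocol and SAP*

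**What the plan says.** All references are to the combined protocol and SAP.

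- **Imputation (8.2.2).** The rule for gaps is: "if necessary, imputation of missing data will be performed according to the last value carried forward method". The same bullet opens by making the calculation apply to everyone: "For each patient, the outcomes will be calculated according to all data available". No outcome or time point is excluded.
- **Sustained pain freedom (3.1, secondary outcome 4).** Besides a 2-hour score of Grade 0, the definition requires a course "with no use of rescue medication and no relapse of headache pain within the 24 hours after the beginning of the e-TNS session".
- **Analysis set (8.2.3).** The only post-baseline data condition for the mITT set is the fourth: "The headache pain severity score OR the migraine associated symptom(s) at 2 hours were reported in the diary". Nothing is required at 24 hours.
- **Measurement (7.1).** After 2 hours, pain has one further scheduled entry, at 24 hours. On rescue, "The patient will also record whether he/she took ANY acute rescue medication during the 24 hours following the beginning of the e-TNS session"; this item appears in the 7.1 table at 24 hours only.
- **Known rescue use (8.2.3).** If rescue was taken between 2 and 24 hours, the "2-hour value carried forward method in this case) will be applied for the 24-hour time point headache pain severity and migraine associated symptoms". This rule does not address a rescue record that is missing.
- **Discontinuation (4.2.5).** When a patient stops early, "all applicable activities scheduled for the final study visit should be performed at the time of discontinuation". Under 4.2.4 the final visit includes handing in the diary.

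**The concern.** Sustained pain freedom asks what happened between 2 and 24 hours. Carrying the 2-hour grade forward answers that question with the value from the start of the interval. For a patient at Grade 0 at 2 hours, the truth can only equal the imputed result or be worse, so the imputation can raise the sustained rate and never lower it. At 2 hours the same method is conservative, because it carries forward a Grade 2 or 3 baseline.

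The stake is the 24-hour estimate. Section 2 includes the 24-hour course in the main objective, and section 1 says the pilot should provide data to prepare a phase 3 trial. With a single arm, no control rate carries the same distortion and offsets it.

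**Working it through.** **The plan's own figures.** The inputs in 8.2.1 are 7.7% and 32.2% pain-free at 2 hours, 80% power and a 5% level (two-sided under 8.2.2). The pooled two-proportion formula gives

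n = [1.960 × √(2 × 0.1995 × 0.8005) + 0.842 × √(0.077 × 0.923 + 0.322 × 0.678)]² / 0.245² = 40.6, so 41 per arm.

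This is close to the stated 42, at which power is 81.4%. Inflating for loss gives 42 / (1 − 0.30) = 60, as stated. That this is a two-arm formula is a separate matter; only N = 42 and the 32.2% rate are used below. The plan gives no figure for sustained pain freedom.

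**What the rules do.** Take an mITT patient observed at Grade 0 at 2 hours.

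| 24-hour grade | Rescue record | Result under the plan | Secondary outcome 4 |
|---|---|---|---|
| blank | use recorded | fails the definition whatever grade is imputed | not sustained |
| blank | no use recorded | Grade 0 carried forward | success, with no relapse imputed |
| blank | blank | Grade 0 carried forward; no rule for rescue | success if the blank is read as no use; otherwise undefined |
| Grade 0 | blank | no rule for rescue | success if the blank is read as no use; otherwise undefined |

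In the last two rows, reading the blank as no use also counts the patient as 'no rescue' in secondary outcome 3.

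**How such a patient arises.** There are two routes: a returned diary with an empty 24-hour section, or a diary handed in at discontinuation before 24 hours.

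**Size.** Expected pain-free at 2 hours: 42 × 0.322 = 13.5, taken as 13. Let m of these lack 24-hour data, and let s be the share who truly sustain, assumed equal in patients with and without data. Neither m nor s is in the documents. In table rows 2 to 4, with blanks read as no use:

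- true rate = 13s / 42
- carried forward = [s(13 − m) + m] / 42
- scored as non-success = s(13 − m) / 42
- gap between the two rules = m / 42
- error of carrying forward = +m(1 − s) / 42
- error of non-success scoring = −ms / 42

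With s = 0.60, the true rate is 7.8/42 = 18.6%.

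| m | Carried forward | Non-success | Gap (points) | Error, carried forward | Error, non-success |
|---|---|---|---|---|---|
| 1 | 8.2/42 = 19.5% | 7.2/42 = 17.1% | 2.4 | +1.0 | −1.4 |
| 2 | 8.6/42 = 20.5% | 6.6/42 = 15.7% | 4.8 | +1.9 | −2.9 |
| 3 | 9.0/42 = 21.4% | 6.0/42 = 14.3% | 7.1 | +2.9 | −4.3 |
| 4 | 9.4/42 = 22.4% | 5.4/42 = 12.9% | 9.5 | +3.8 | −5.7 |

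**Sensitivity to s.** With m = 2, carrying forward overstates by 2 × 0.2/42 = 1.0 point if s = 0.80, and by 2 × 0.5/42 = 2.4 points if s = 0.50. If none of the patients without data sustained, the overstatement equals the whole gap, m/42.

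**The case against.** The best case against runs as follows.

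- **Missing entries should be few.** The investigator reviews the diary in detail at the final visit, about 4 days after treatment (4.2.4), and missing data trigger queries (8.1). This stands as a reason to expect small m. It is not a scoring rule, and 8.2.2 itself provides for data that remain missing.
- **Non-success scoring can be further from the truth.** With s = 0.60 it errs by −2.9 points at m = 2, against +1.9 for carrying forward. This stands, and holds whenever s exceeds one half and data are missing at random. It argues for showing both bounds, not for keeping an imputation that assumes the answer.
- **The effect is small beside sampling error.** A Wilson 95% interval for 8/42 runs from about 10% to 33%. This stands too. The outcome is secondary, in an open-label pilot.

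A reader might also infer more than the documents support:

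- *That the plan scores a blank rescue record as no use.* No section says so. Carrying forward cannot supply a rescue value, so on this item the plan is silent.
- *That every patient lost after treatment becomes a success.* Clinical data are on paper (7.1). A patient who never returns the diary supplies no baseline or 2-hour entry, fails mITT conditions 3 and 4, and leaves the denominator.
- *That the 30% loss measures missing 24-hour data.* It takes 60 down to 42, so the 42 are already net of it.
- *That 4.8 points is the bias.* It is the distance between two scoring rules at m = 2, and equals the bias only if neither patient sustained.
- *That secondary outcome 4 alone addresses durability.* Secondary outcome 3 covers rescue from 2 to 24 hours, and pain and symptoms are recorded at 24 hours.

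**Conclusion.** The point holds in a limited form. As written, 8.2.2 lets an unobserved 24-hour grade satisfy the no-relapse condition for a patient who was pain-free at 2 hours. Where the rescue record is blank, the plan leaves secondary outcomes 3 and 4 undefined, and the reading that favours the device is open.

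On the stated assumptions (42 evaluable, 13 pain-free at 2 hours, 60% truly sustaining, data missing at random, blank rescue read as no use), the overstatement is about 1.9 points for 2 affected patients and about 1 to 4 points for 1 to 4. The documents give no rate of missing 24-hour data, so these figures are illustrations and not forecasts. Neither primary outcome nor the sample size is affected. The change is still worth making, because the direction for sustained pain freedom is fixed in advance and the correction is cheap.

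**What to change.** In 8.2.2:

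1. Exempt secondary outcomes 3 and 4 from last value carried forward.
2. Count sustained pain freedom as a success only if the 24-hour pain grade and the rescue record are both present and meet the definition.
3. Report the number of patients with missing 24-hour data, and give the sustained rate with those patients counted as successes and as non-successes.
4. For rescue use, give the rate with missing records counted as 'yes' and as 'no'.

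The cost is a few sentences. No visit, procedure or change in sample size follows. The drawback is that the main sustained pain-freedom figure becomes conservative and may understate the true rate, which is why both bounds should stand beside it.

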#### 8.2.3. Statistical analysis

Modified intention-to-treat (mITT) analysis

Patient data will be included in the mITT analysis if all the four following conditions are met:

- 1. The patient treated a qualifying migraine.
- 2. The patient applied the Cefaly® Abortive Program treatment during at least one minute\*.
- 3. The headache pain severity score **AND** the migraine associated symptom(s) at baseline were reported in the diary.
- 4. The headache pain severity score **OR** the migraine associated symptom(s) at 2 hours were reported in the diary.

Data provided by Colucid Pharmaceuticals, Inc. and available on the following website: https://globenewswire.com/news-release/2016/09/06/869611/0/en/CoLucid-Pharmaceuticals-Announces-Achievement-of-Both-Primary-and-Key-Secondary-Endpoints-in-the-SAMURAI-Phase-3-Pivotal-Trial-of-Lasmiditan-in-Migraine.html (consulted in May 2017).

\*If the patient stopped the 2-hour treatment session before its end for any reason, he/she is kept in the modified intention-to-treat (mITT) analysis if all the other conditions are met.

If the patient takes rescue medication between 2 hours and 24 hours after the beginning of the e-TNS session, the headache pain intensity and associated symptoms presence can be affected by the medication and the last value carried forward method (2-hour value carried forward method in this case) will be applied for the 24-hour time point headache pain severity and migraine associated symptoms.

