- [name], at Columbia University, implemented an open-label pilot trial on the acute treatment of migraine with the Cefaly® e-TNS device (6). Thirty (30) patients having a migraine attack with or without aura were included in the modified intention-to-treat (mITT) analysis. In terms of safety, no adverse events or side effects were reported. In terms of efficacy, mean pain intensity was significantly reduced by 57.10% after the 1-hour e-TNS treatment (-3.22 ± 2.40; p<0.001) and by 52.84% at 2-hour time point (-2.98 ± 2.31; p<0.001). No patients took rescue medications within the 2-hour observation phase. Within the 24-hour follow-up, 34.62% of patients used a rescue medication. The findings from this open-label study suggest that e-TNS with the Cefaly® device is a safe and effective acute treatment for migraine, and merits further study with a double-blind, randomized, sham-controlled trial.

- University of Liege in Belgium (Prof. [name]) did a post-marketing survey on more than 800 regular users of the Cefaly® device in France, Switzerland and Belgium (7). 89.2% of responders to the questionnaire had been diagnosed by a physician as suffering from migraine. 88.6% of these patients reported to use the Cefaly® device during migraine attacks and that in 42.6% of these attacks, the use of the Cefaly® device prevented the intake of acute anti-migraine medication.

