# 2. Study objective

The main objective of this study is to have a pilot assessment of the efficacy of the Cefaly® Abortive Program device used at home for 2 hours to treat a migraine attack, as triptans are generally used. That is to say having pilot data to assess the efficacy of the Cefaly® Abortive Program device in the abortive treatment of acute migraine as measured by 2-hour pain freedom, pain relief and migraine associated symptoms freedom, plus evolution of these measurements for 24 hours after the beginning of the treatment session.

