4.2.3. Post-treatment phase

Two hours after the beginning of the treatment session, the patient is allowed to take rescue medication

if the migraine headache pain is still moderate or severe, or if after initial pain relief (no headache or

mild headache pain) a moderate or severe headache is resuming.

The patient will have to note the headache pain severity in his/her diary at 24 hours after the beginning

of the treatment session (24-hour data), as well as the migraine associated symptoms. Patients will also

be instructed to record in their diary the rescue medication intake, if any, during the 24 hours following

the beginning of the treatment session.

In his/her AE collecting form, the patient will record any adverse event occurring during the 24 hours

following the beginning of the treatment and is instructed to notify the investigator immediately for any

serious or severe adverse experience with the stimulation.

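### In the descriptive 24-hour pain summaries, carrying the 2-hour grade forward for rescue users shows a patient who relapsed after relief as still pain-free or relieved

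*Combined protocol and SAP*

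**What the plan says.** Section 8.2.3 gives its reason first: rescue medication can alter the later ratings. It then sets the rule: "2-hour value carried forward method in this case) will be applied for the 24-hour time point headache pain severity and migraine associated symptoms". The only trigger is rescue intake after 2 hours. The 2-hour grade plays no part.

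Section 4.2.3 allows rescue from 2 hours in two situations. One is pain that is still moderate or severe. The other is a return of pain after initial relief, where the text ends "mild headache pain) a moderate or severe headache is resuming". Section 6.5 states the pain condition more briefly: a patient with "headache pain (Grade 2 or 3), he/she is allowed to take his/her own anti-migraine rescue medication". Only section 4.2.3 speaks of resumed headache.

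The 24-hour pain data are meant to be reported. The objective in section 2 names pain freedom, pain relief and symptom freedom at 2 hours, "plus evolution of these measurements for 24 hours after the beginning of the treatment session". The table in section 7.1 schedules pain severity at 24 hours, and section 8.2.2 says that "efficacy data will be descriptively summarized at each time point".

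On rescue itself, section 7.1 says: "The patient will also record whether he/she took ANY acute rescue medication during the 24 hours following the beginning of the e-TNS session". No pain grade is scheduled at the moment of intake.

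**The concern.** The carry-forward rule treats two different kinds of rescue user alike. One never improved, and for that patient the 2-hour grade describes the device's result fairly. The other improved, lost the improvement and then took medication. For that patient, carry-forward removes the drug effect but also removes the relapse that led to the drug.

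At stake is how the 24-hour pain-grade table and the 24-hour pain-freedom and pain-relief rates read. Section 1 says this pilot should supply data for a later controlled trial, so an optimistic picture of how long relief lasts could carry over into its planning. The outcome list in section 3.1 has a sustained outcome for pain freedom but none for pain relief, so a loss of relief from Grade 1 appears in no listed sustained outcome.

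**Working it through.** **Step 1. Denominator.** Section 8.2.1 plans at least 60 patients and allows for 30% loss. 60 x (1 - 0.30) = 42, which matches the plan's 42 evaluable patients. I use 42, and 60 as the case with no loss.

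**Step 2. Apply the rule to a rescue user at each 2-hour grade.** The middle column assumes rescue was taken as section 4.2.3 permits.

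| Grade at 2 h | Pain when rescue is taken | Grade tabulated at 24 h | Reads as |
|---|---|---|---|
| 0 | resumed, Grade 2-3 | 0 | pain-free and relieved |
| 1 | resumed, Grade 2-3 | 1 | relieved |
| 2 | still Grade 2-3 | 2 | not relieved |
| 3 | still Grade 2-3 | 3 | not relieved |

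The last two rows are as they should be. The first two are the problem.

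**Step 3. Effect per patient.** Compared with counting rescue as non-response, each patient in the first two rows adds one responder to the 24-hour pain-relief rate:

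- 1/42 = 2.4 percentage points
- 1/60 = 1.7 percentage points

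A patient in the first row adds the same amount to the 24-hour pain-freedom rate.

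**Step 4. Illustration.** The number of such patients is my assumption. With 42 analysed:

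- 1 patient: 1/42 = 2.4 points
- 3 patients: 3/42 = 7.1 points
- 5 patients: 5/42 = 11.9 points

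The documents cannot narrow this range. For the earlier open-label pilot, section 1 reports: "Within the 24-hour follow-up, 34.62% of patients used a rescue medication". It does not split those patients by 2-hour grade, and that pilot used a 1-hour session.

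**Step 5. Outcomes that do not move.** Both primary outcomes and the 2-hour secondary outcomes use 2-hour data only. Rescue use is counted directly. Sustained pain freedom is defined "with no use of rescue medication and no relapse of headache pain within the 24 hours", so documented rescue excludes the patient whatever grade is carried forward. The effect on each of these is 0.

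**Step 6. Associated symptoms.** Rescue is permitted on pain grade alone. A symptom absent at 2 hours may or may not have been present when rescue was taken, and nothing scheduled records it. Carrying forward absence may be right or wrong.

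**The case against.** The strongest reply is that nothing listed is harmed. Section 3.1 defines no 24-hour pain-relief rate. The two listed outcomes that reach 24 hours, rescue use and sustained pain freedom, already handle rescue properly, and no 24-hour comparison is specified in this single-arm pilot. That stands, and it is why the point is minor. It does not remove the point. The objective and section 8.2.2 call for the 24-hour summaries, and an overall rescue percentage does not tell the reader which 2-hour responders relapsed.

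A second reply is that the relapse is inferred. Section 4.2.3 gives a permission, and no grade is recorded at intake, so a patient might take rescue for mild pain. This also stands. The misreporting is certain only for patients who took rescue as the protocol permits.

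A third is that the rule is conservative, since it refuses to credit the device with the drug's effect. That is true for patients still at Grade 2 or 3 at 2 hours, and any change must keep it. It does not help patients who had been relieved.

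A reader might go further and infer that associated symptoms are also shown falsely as absent. The documents do not support this. They leave symptom status after rescue unknown, and treating every rescue user as a symptom non-responder would swap one possible bias for another.

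**Conclusion.** The point holds as a minor one, confined to the descriptive 24-hour pain-grade, pain-freedom and pain-relief summaries. The per-patient size follows from the plan's own denominators. The total is unknown because the number of patients who relapse from Grade 0 or 1 and take rescue is not given. The conclusion rests on two assumptions: those patients follow the rescue condition in section 4.2.3, and the fair comparison is to count rescue as non-response.

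Two stronger readings are tempting. One is that the trial's efficacy result is inflated; it is not, because the primary and listed secondary outcomes do not depend on the carried-forward grade when rescue is documented. The other is that carry-forward after rescue favours the device throughout; it does not, because for patients never relieved it gives the same relief result as counting them as non-responders.

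**What to change.** Replace the carry-forward sentence in section 8.2.3 with:

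*In the 24-hour pain-freedom and pain-relief rates, patients who took rescue medication between 2 and 24 hours stay in the denominator and are counted as non-responders. In the 24-hour pain-grade and symptom frequency tables they are shown in a separate row, 'rescue medication taken', broken down by 2-hour status; neither the 2-hour value nor the post-rescue rating is used as their 24-hour value.*

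This keeps the drug effect out, makes relapses visible, and makes no claim about symptoms that the data cannot support. It needs no new data, since rescue intake and 2-hour status are already in the diary, and it leaves the rescue permission untouched.

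The cost is that the 24-hour pain rates become slightly less favourable, by 1.7 to 2.4 points per affected patient. A patient who took rescue for only mild pain would also count as a non-responder.
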